### 4.2.2 PROTOCOL ADHERENCE

We have defined protocol deviation *a priori* as delivered UFNET rate that lies  $>0.5$  mL/kg/h outside of the target UFNET rate range in the assigned treatment group for greater than six consecutive hours during fluid removal *without* significant changes in MAP (*i.e.*, MAP  $< 65$  mmHg or  $\geq 90$  mmHg). As such, out of range UFNET rates  $>0.5$  mL/kg/h beyond the target UFNET rate range in the assigned treatment group will not constitute a protocol deviation when the bedside team titrated the UFNET rate as required to manage the patient hemodynamics (*i.e.*, when clinicians appropriately decreased rate or stopped fluid removal for hypotension; increased fluid removal rate for hypertension or for treatment of respiratory distress due to fluid overload and pulmonary edema).

We will report the following stratified by restrictive and liberal UFNET rate groups: i.) no. of occurrences of deviations for six consecutive hours divided by UFNET days (mean events per day); ii.) no. of days with UFNET out of range for at least six consecutive hours; iii.) no. of patients with at least one occurrence of UFNET rate out of range for six consecutive hours. The proportion of patients with protocol deviation will be compared using the Wald test for GLMM and adjusted for prespecified covariates.

As an exploratory analysis, we will also report the proportion of total hours of UFNET rate within, above, or below range for each patient weighted equally and proportionally to total hours of fluid removal.

#### 4.2.3 RECRUITMENT RATE

A successful recruitment rate will be defined as achieving an enrollment rate of 2 patients per month per center during the trial. The recruitment metric will be calculated as the mean number (standard deviation) of recruited patients per active screening month.

### 4.3 ANALYSIS METHODS FOR SECONDARY AND SAFETY OUTCOMES

We will use GLMM regression after adjusting for various prespecified variables. We will consider observed differences between groups to be statistically significant at a two-sided, nominal alpha of 0.05 for all outcomes.

For binary outcomes, we will use the Wald test for GLMM to compare the proportion of patients in the two UFNET rate groups (Appendix A).

For continuous variables, we will report incident rate ratios calculated with zero-truncated negative binomial regression modeling adjusted for prespecified baseline covariates.

For independence from KRT and hospital mortality, we will fit GLMM regression models and report odds ratios with corresponding 95% confidence intervals from logistic regression after adjusting for prespecified baseline covariates. To safeguard against erroneous type I error inflation in secondary outcomes, we will apply the conservative Hochberg procedure for adjustment on multiplicity to two key secondary outcomes of mortality and KRT dependence. Because of the potential for type I error due to multiple comparisons, findings for analyses of the other secondary end points will be interpreted as exploratory.

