## 2 STUDY OVERVIEW

This document is the Statistical Analysis Plan for the RELIEVE-AKI study. The document describes the statistical methods used to analyze the primary, secondary and safety outcomes in the study. Appendix A is a list of all variables that will be analyzed in the study along with their classification and analysis method. Appendix B is the definition of all derived and composite variables and the data imputation rules for all variables where imputation is used. Appendix C shows the shell tables.

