#### 3.5.3 SAFETY OUTCOMES

1. No. of intradialytic hypotensive episodes
2. No. of intradialytic hypertensive episodes
3. No. of intradialytic new onset cardiac arrhythmias including supraventricular tachycardia, bradycardia, atrial fibrillation, ventricular tachycardia, ventricular fibrillation, and cardiac arrest
4. No. of participants with emergent use of rescue  $UF_{NET}$  with rates higher than the assigned treatment arm
5. No. of participants with severe hypophosphatemia ( $<0.5$  mg/dL)
6. No. of participants with severe hypokalemia ( $<3.0$  mg/dL)
7. No. of participants with severe hypocalcemia ( $<1.90$  mg/dL or ionized calcium  $<0.90$  mmol/L)
8. No. of episodes of stopping CKRT due to filter clotting or clogging
9. No. of participants with discontinuation of  $UF_{NET}$  due to hemodynamic instability
10. No. of participants in whom surgical wounds are left open due to edema
11. No. of participants with new organ dysfunction
12. No. of participants with worsening of systolic or diastolic cardiac function on echocardiogram
13. No. of participants with worsening of pulmonary edema on chest X Ray and/or CT scan
14. No. of participants with worsening of ileus on abdominal X Ray and/or CT scan
15. No. of participants with bowel ischemia or anastomotic breakdown based on intraoperative findings
16. No. of participants with pressure ulcerations
17. No. of participants with new wound infections
18. No. of participants with new arterial or venous thrombosis
19. No. of participants with severe anemia requiring red cell transfusions

20. No. of participants with severe thrombocytopenia requiring platelet transfusions
21. No. of participants with new secondary infections

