## 4 DATA ANALYSIS PLAN

### 4.1 OVERALL ANALYTICAL PLAN

All analyses will be performed on an intention-to-treat basis, which generally biases toward no difference. We will also perform per-protocol analyses where the assigned intervention was followed. We will first examine the data structure, distributions of the outcomes and explanatory variables, and potential missing data elements. Missing data will be imputed after examining the reason for missingness. For data that are missing completely at random or missing related to other collected covariates, we will use the multivariable imputation by chained equation (MICE) to impute data before fitting models.

The individual ICU is the unit of randomization, and the individual patient is the unit of analysis. In SW-CRT, the usual comparisons between two treatments need to be made over a differing time making standard group comparison-based methods biased and potentially ineffective. Therefore, we will use adjusted generalized linear mixed models (GLMM) for all primary and secondary outcomes, as delineated by Hussey and Hughes and others, to account for temporal and clustering effects typically encountered in SW-CRT designs. In these models, we will use the ICU as random effects. Time will be treated as random in the main analysis but will also be treated as fixed effects and interact with other covariates.

We will adjust all analyses for prespecified variables such as age, baseline eGFR, severity of illness as measured by the acute physiology and chronic health evaluation (APACHE)-III score, Elixhauser Comorbidity Index score, use or nonuse of mechanical ventilation, admission source, percentage of fluid overload before study enrollment, presence or absence of sepsis, baseline cardiovascular SOFA score and any other variable that are associated with outcome of  $UF_{NET}$  and had a between-group difference ( $P \leq 0.2$ ) on univariable analysis. We will assess the stability of final models using routine model diagnostics to identify potential outliers and/or influential observations. We will report both

adjusted and unadjusted analyses stratified by restrictive and liberal UFNET groups.

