## 5 APPENDICES

### 5.1 APPENDIX A: OUTCOME VARIABLES AND ANALYSIS METHOD

Variable	Outcome Category	Scale	Analysis Method
Between-group separation in mean delivered UF NET rates	Primary	Continuous	GLMM
Protocol deviation	Primary	Binary	Wald-test for GLMM
Recruitment rate	Primary	Continuous	GLMM
Daily fluid balance	Secondary	Continuous	GLMM
Cumulative fluid balance	Secondary	Continuous	GLMM
Duration of kidney replacement therapy	Secondary	Continuous	GLMM
Duration of mechanical ventilation	Secondary	Continuous	GLMM
Organ failure free days	Secondary	Continuous	GLMM
ICU length of stay	Secondary	Continuous	GLMM
Hospital length of stay	Secondary	Continuous	GLMM
Hospital mortality	Secondary	Binary	Wald-test for GLMM
Dialysis dependence at hospital discharge	Secondary	Binary	Wald-test for GLMM
Hypotensive episodes	Safety	Continuous	GLMM
Hypertensive episodes	Safety	Continuous	GLMM
Cardiac arrhythmias	Safety	Continuous	GLMM
Emergent use of rescue UF NET rates	Safety	Binary	Wald-test for GLMM
Severe hypophosphatemia	Safety	Binary	Wald-test for GLMM
Severe hypokalemia	Safety	Binary	Wald-test for GLMM
Severe hypocalcemia	Safety	Binary	Wald-test for GLMM
CKRT stopping due to hemofilter clotting or clogging	Safety	Continuous	GLMM
Discontinuation of fluid removal due to hemodynamic instability	Safety	Binary	Wald-test for GLMM
Inability to close surgical wounds	Safety	Binary	Wald-test for GLMM
New organ dysfunction	Safety	Binary	Wald-test for GLMM
Worsening systolic/diastolic cardiac function	Safety	Binary	Wald-test for GLMM

Worsening pulmonary edema	Safety	Binary	Wald-test for GLMM
Worsening of ileus	Safety	Binary	Wald-test for GLMM
Bowel ischemia or anastomotic breakdown	Safety	Binary	Wald-test for GLMM
Pressure ulcerations	Safety	Binary	Wald-test for GLMM
New wound infections	Safety	Binary	Wald-test for GLMM
New arterial or venous thrombosis	Safety	Binary	Wald-test for GLMM
Severe anemia	Safety	Binary	Wald-test for GLMM
Severe thrombocytopenia	Safety	Binary	Wald-test for GLMM
New secondary infections	Safety	Binary	Wald-test for GLMM

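### The zero-truncated negative binomial that SAP 4.3 names for continuous secondary and safety outcomes does not suit 9 of the 11 it covers

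*SAP*

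**What the plan says.** SAP 4.3, which covers secondary and safety outcomes, opens with GLMM regression and then gives this rule: "For continuous variables, we will report incident rate ratios calculated with zero-truncated negative binomial regression modeling adjusted for prespecified baseline covariates". Logistic regression is named only for hospital mortality and independence from KRT. No normal, untruncated count, zero-inflated or hurdle model is named for any continuous outcome.

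SAP 2 makes Appendix A the reference for methods: "Appendix A is a list of all variables that will be analyzed in the study along with their classification and analysis method". Appendix A classes seven secondary and four safety outcomes as continuous, including the row "Hypotensive episodes", and gives the method for each only as GLMM. SAP 4.1 is equally general: "we will use adjusted generalized linear mixed models (GLMM) for all primary and secondary outcomes". The same section also states: "All analyses will be performed on an intention-to-treat basis".

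SAP 3.5.3 defines the safety outcomes in question as counts, for example "No. of intradialytic hypotensive episodes" and "No. of episodes of stopping CKRT due to filter clotting or clogging". The footnote to the safety shell table (SAP 5.3.3, Table 3) gives a different analysis: its P values compare the share of patients who had each event.

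**The concern.** A zero-truncated negative binomial gives no probability to zero or to negative values. Fluid balance in mL is signed, so the one model named for it cannot be fitted. The analyst of an unblinded trial would have to choose a replacement, possibly with the data in hand.

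For outcomes that can be zero, the model can be fitted only to patients with a positive value. Event-free patients drop out, against the intention-to-treat statement. The resulting rate ratio describes frequency among patients who had at least one episode and does not show whether treatment prevents episodes. Hypotension and arrhythmia are two of the affected counts, and the central hypothesis (SAP 3) is that the restrictive strategy reduces both.

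For the four safety counts, SAP 4.3, Appendix A and the Table 3 footnote also give instructions that do not agree.

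**Working it through.** The plan gives no figure on this point to reproduce. The check sorts the outcomes by the values they can take, then sizes the consequence.

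**1. Which outcomes fit the named model**

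The model is P(Y = y | Y > 0) = P_NB(y) / (1 − P_NB(0)) for y = 1, 2, 3, … It is zero for every y ≤ 0.

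| Continuous outcome (Appendix A) | Possible values | Basis | Fits? |
|---|---|---|---|
| Daily and cumulative fluid balance (2) | Signed mL | Negative daily balance is an expected result (Protocol 5.4.1); shell Table 2 reports mL including UF volume | No |
| Ventilation duration | Can be 0 | A covariate is "use or nonuse of mechanical ventilation" (SAP 4.1) | No |
| Organ-failure-free days | Can be 0 | Day count with no minimum (SAP 5.2.1.4) | No |
| Hypotensive, hypertensive, arrhythmia and filter-clotting episodes (4) | Can be 0 | Episode counts (SAP 3.5.3) | No |
| KRT duration | 0 only if CKRT never starts | Patients for whom CKRT is only intended are eligible (Protocol 4 and 6.5), and enrollment is at consent (Protocol 6.8) | Conditional |
| ICU and hospital stay (2) | Normally 1 or more | – | Yes, if counted in whole days from 1 |

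Total: 7 secondary + 4 safety = 11. Unsuitable: 2 signed + 6 plainly able to be zero + 1 conditionally able to be zero = 9.

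**2. How many patients a truncated hypotension model would leave out**

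Patients left out = N × (1 − proportion with hypotension). N is 112 in the protocol and 144 in the SAP. The proportions come from Protocol 5.2.5 (43.2% and 64.6%) and 5.1.4 (19% to 97%).

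| With hypotension | Left out of 112 | Left out of 144 |
|---|---|---|
| 43.2% | 112 × 0.568 = 63.6 | 144 × 0.568 = 81.8 |
| 64.6% | 112 × 0.354 = 39.6 | 144 × 0.354 = 51.0 |
| 19% | 112 × 0.81 = 90.7 | 144 × 0.81 = 116.6 |
| 97% | 112 × 0.03 = 3.4 | 144 × 0.03 = 4.3 |

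These are indicative only, because the cited cohorts do not define hypotension as SAP 5.2.2.1 does.

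**3. What the truncated ratio can miss (assumed effect on occurrence)**

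Mean episodes per patient = P(any episode) × mean episodes among those affected. The all-patient ratio is therefore the product of two ratios, and the truncated model uses information only from the second.

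Assume that the proportion with any hypotension falls by 20%, from 43.2% to 34.56%, and that episodes per affected patient do not change:

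- All-patient ratio = (0.3456 / 0.432) × 1 = 0.80.
- Truncated ratio = 1.00.

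Simulation with 1 + Poisson(1) episodes in affected patients gave:

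| Per arm | Untruncated | Truncated |
|---|---|---|
| 3000 | 0.80 | 1.00 |
| 56 (400 runs) | 0.78 | 0.97 |
| 72 | 0.80 | 1.00 |

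A second set of assumptions used 43% versus 30% affected, 1 + Poisson(2) episodes if affected, and 56 per arm. The true ratio was 0.30 / 0.43 = 0.70. The untruncated model gave 0.69. The truncated model gave 0.98 and kept about 41 of 112 patients.

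The reverse case is kinder to the truncated model. If only the episodes per affected patient fell by 20%, the all-patient ratio would again be 0.80 and the truncated model would detect the fall.

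**4. What is lost when the negative binomial is true**

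Assume a true negative binomial with dispersion 1 and ratio 0.70 (400 runs). Both models centre near 0.70, so only precision is lost. The SE of the log ratio changes as follows:

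| With events in controls | Per arm | Untruncated SE | Truncated SE |
|---|---|---|---|
| 43.2% | 56 | 0.32 | 0.49 |
| 43.2% | 72 | 0.28 | 0.45 |
| 64.6% | 56 | 0.25 | 0.29 |
| 64.6% | 72 | 0.22 | 0.27 |

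The truncated SEs are not stable to two decimals. Repeat runs gave about 0.53 for the first row, 0.46 for the second and 0.32 to 0.33 for the third, so the table somewhat understates the loss. All simulations ignore clustering, time and covariates.

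**The case against.** The strongest reply is that the sentence in 4.3 is loosely worded. An incident rate ratio has no meaning for mL, SAP 4.1 and Appendix A prescribe GLMM throughout, and a linear mixed model for fluid balance would satisfy both. The ICU random effect and the listed covariates are already set, and the wording can be corrected before analysis. This shows that the fix is easy, but GLMM is a class of models. No family is named for any continuous outcome except the unsuitable one.

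Second, the Table 3 footnote keeps event-free patients in the P values for the four safety counts, and that table has no rate-ratio column. This stands, and it limits the harm because an any-event difference would still be visible. It does not resolve the conflict with 4.3 and Appendix A. An any-event test and a truncated count model could together form a hurdle model, but the SAP does not say so.

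Third, a zero KRT duration needs an enrolled patient who never starts CKRT. The protocol requires an intention to remove fluid for at least 48 hours and initiation within 24 hours of enrollment. Such zeros should be uncommon. Without KRT duration the count is 8 of 11, and the conclusion is the same.

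Fourth, the SAP nowhere says that patients with zeros will be excluded. That is correct. The exclusion follows from fitting the named model.

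Fifth, secondary end points other than mortality and KRT dependence are exploratory (SAP 4.3), and the trial is not powered for adverse events (Protocol 11.3). This limits the weight of the point.

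**Conclusion.** The concern holds. The only family named for continuous secondary and safety outcomes is unsuitable for 9 of 11: two cannot be fitted, six can plainly be zero, and one can be zero in uncommon circumstances. Only ICU and hospital stay suit truncation.

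For hypotension, the truncated model would set aside roughly 40 to 64 of 112 patients (51 to 82 of 144) at the two cited cohort rates. These figures assume that the rates carry over to the SAP definition. The effect on the estimate depends on how treatment acts. A pure effect on occurrence would be missed (0.80 read as 1.00), an effect on episodes per affected patient would be detected, and under a true negative binomial only precision suffers.

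The primary outcomes, mortality and KRT dependence are not affected. This should be corrected before analysis, but it does not threaten the trial's main conclusions.

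**What to change.** Replace the single rule in SAP 4.3 and state the family and link for each row of Appendix A:

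- **Fluid balance:** linear mixed model, reported as a mean difference in mL.
- **Four episode counts:** untruncated negative binomial mixed model on all patients, or a hurdle model stated as such.
- **Ventilation duration, organ-failure-free days, KRT duration:** a model that admits zeros, for example proportional-odds or two-part.
- **ICU and hospital stay:** truncation may stay if whole days counted from 1 are specified.

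Reconcile SAP 4.3, Appendix A and the Table 3 footnote so that each safety count has one stated analysis. Optionally, add a rate per time at risk over the adjudication window in SAP 5.2.2 as a sensitivity analysis, not as a substitute for the all-patient count comparison.

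The cost is SAP text and programming. No further data, patients or visits are needed.

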#### 4.4 HANDLING THREATS TO DATA ANALYSIS

Potential threats include missing data, handling of subject data for individuals who withdraw from the study, and incorrect enrollment. We expect incorrect enrollment to be very rare. Missing data, from either incomplete data entry or subject withdrawal, present a greater challenge. We will minimize missingness by creating a concise web-based data collection form, incorporating extensive logic checks to prevent erroneous data entry, auto-prompts for missingness, and close site coordination. We will apply methods for missingness analyses based on weighted estimating equations, multiple imputations using methods proposed by Rubin and Schenker, and/or pattern mixture models.

## 5 APPENDICES

### 5.1 APPENDIX A: OUTCOME VARIABLES AND ANALYSIS METHOD

Variable	Outcome Category	Scale	Analysis Method
Between-group separation in mean delivered UF NET rates	Primary	Continuous	GLMM
Protocol deviation	Primary	Binary	Wald-test for GLMM
Recruitment rate	Primary	Continuous	GLMM
Daily fluid balance	Secondary	Continuous	GLMM
Cumulative fluid balance	Secondary	Continuous	GLMM
Duration of kidney replacement therapy	Secondary	Continuous	GLMM
Duration of mechanical ventilation	Secondary	Continuous	GLMM
Organ failure free days	Secondary	Continuous	GLMM
ICU length of stay	Secondary	Continuous	GLMM
Hospital length of stay	Secondary	Continuous	GLMM
Hospital mortality	Secondary	Binary	Wald-test for GLMM
Dialysis dependence at hospital discharge	Secondary	Binary	Wald-test for GLMM
Hypotensive episodes	Safety	Continuous	GLMM
Hypertensive episodes	Safety	Continuous	GLMM
Cardiac arrhythmias	Safety	Continuous	GLMM
Emergent use of rescue UF NET rates	Safety	Binary	Wald-test for GLMM
Severe hypophosphatemia	Safety	Binary	Wald-test for GLMM
Severe hypokalemia	Safety	Binary	Wald-test for GLMM
Severe hypocalcemia	Safety	Binary	Wald-test for GLMM
CKRT stopping due to hemofilter clotting or clogging	Safety	Continuous	GLMM
Discontinuation of fluid removal due to hemodynamic instability	Safety	Binary	Wald-test for GLMM
Inability to close surgical wounds	Safety	Binary	Wald-test for GLMM
New organ dysfunction	Safety	Binary	Wald-test for GLMM
Worsening systolic/diastolic cardiac function	Safety	Binary	Wald-test for GLMM

Worsening pulmonary edema	Safety	Binary	Wald-test for GLMM
Worsening of ileus	Safety	Binary	Wald-test for GLMM
Bowel ischemia or anastomotic breakdown	Safety	Binary	Wald-test for GLMM
Pressure ulcerations	Safety	Binary	Wald-test for GLMM
New wound infections	Safety	Binary	Wald-test for GLMM
New arterial or venous thrombosis	Safety	Binary	Wald-test for GLMM
Severe anemia	Safety	Binary	Wald-test for GLMM
Severe thrombocytopenia	Safety	Binary	Wald-test for GLMM
New secondary infections	Safety	Binary	Wald-test for GLMM

## 5.2 APPENDIX B: DERIVED VARIABLES

### 5.2.1 OUTCOME VARIABLES

#### 5.2.1.1 *Delivered UFNET rate*

The delivered UFNET rate variable is defined as net intravascular fluid removal rate from the patient after accounting for intravenous fluids infused in the current hour and adjusted for predicted body weight. The overall mean delivered UFNET rate for each hour will be calculated from all patients enrolled in the restrictive and liberal group.

#### 5.2.1.2 *Hospital mortality to day 28*

Death prior to discharge alive from study hospital will be counted as hospital mortality. Patients whose final status is unknown but who are known to be alive on study day 28 based on known event dates will be counted as alive.

#### 5.2.1.3 *Kidney replacement therapy to day 28*

Patients receiving any form of kidney replacement therapy 72 hours before discharged alive will be considered dialysis dependent. If a patient dies before day 28, the patient will be considered dialysis dependent. Patients who are not dialysis dependent by day 28 but continue to remain in the hospital or receive dialysis after day 28 will be considered liberated from dialysis.

#### 5.2.1.4 *Organ failure free days to day 28*

Organ failure is defined as present on any date when the most abnormal vital signs or clinically available lab value meets the definition of clinically significant organ failure according to SOFA scores. Patients will be followed for development of organ failures to death, hospital discharge or study day 28, whichever comes first. Each day a patient is alive and free of a given organ failure will be scored as a failure-free day. Any day that a patient is alive and free of all organ failures will represent days alive and free of all organ failure.

##### 5.2.1.4.1 E. SOFA scoring system

Variables	Sequential Organ Failure Assessment Score				
	0	1	2	3	4
Respiratory					
PaO 2 /FiO 2 (mmHg)	>400	≤400	≤300	≤200 a	≤100 a
Coagulation					
Platelets (x 10  /µL)	>150	≤150	≤100	≤50	≤20
Liver					
Bilirubin	<1.2	1.2 – 1.9	2.0 – 5.9	6.0 – 11.9	>12.0

Cardiovascular					
MAP (mmHg)	$\geq 70$	$<70$			
Vasopressor b (doses in mcg/kg/min)			Dopamine $\leq 5$ OR Dobutamine (any dose)	Dopamine $>5$ OR Epinephrine $\leq 0.1$ OR Norepinephrine $\leq 0.1$	Dopamine $>15$ OR Epinephrine $>0.1$ OR Norepinephrine $>0.1$
None	None				
Central Nervous System					
Glasgow Coma Scale	15	13 – 14	10 – 12	6 – 9	$<6$
Kidney					
Creatinine (mg/dL)	$<1.2$	1.2 – 1.9	2.0 – 3.4	3.5 – 4.9 OR $<500$	$\geq 5$ OR $<200$
Urine output (mL/day)					

a Values are with ventilatory support; the maximum score in patients not receiving ventilatory support is 2

b Pressor agents administered for at least 1 hour

We define a clinically significant organ failure as a new SOFA score of  $\geq 2$

We treat post-ICU SOFA as normal; post-ICU means getting out and staying out of ICU

